## 5. Specific Aims

The goal of the proposed research project is to explore the acceptability and efficacy of a combined transcutaneous vagus nerve simulation (tVNS) and mindfulness intervention in enhancing sleep and well-being among college students and compare it to mindfulness-only and control conditions with the hypothesis that the combined intervention will have greater efficacy due to synergistic brain effects of tVNS and mindfulness. In addition to experimental results, the proposed project will

generate effect size data to inform future trials of the combined approach and assess the feasibility and acceptability of our study design.

**Specific Aim 1:** To evaluate the feasibility and acceptability of sustained engagement with the Brightmind mindfulness app among college students.

Research question 1.1: Do students find this app acceptable and engage with it consistently across a 4-week period?

Research question 1.2: What are the barriers and facilitators to sustained engagement with the app?

Hypothesis 1.3: Participants who spend more time engaging with the app will see greater improvements in mental health (e.g., stress, anxiety, depressive symptoms, positive affect) and HRV compared to participants who spend less time engaging with the app.

**Specific Aim 2:** To obtain preliminary effect size data on the efficacy of the Brightmind mindfulness app in improving proximal and distal mental health outcomes among college students

Hypothesis 2.1: Participants in the mindfulness-only group will demonstrate greater improvements in mental health (e.g., stress, anxiety, depressive symptoms, positive affect) than participants in the control group

Hypothesis 2.2: Overnight heart rate variability (HRV), positive affect, and interoceptive awareness will be greater in the mindfulness-only group compared to the control group.

Hypothesis 2.3: HRV will increase from before to after each mindfulness session.

**Specific Aim 3:** Determine feasibility and acceptability of the combined tVNS + mindfulness intervention.

Research question 3.1: Do students find this combined intervention acceptable and demonstrate adequate adherence (i.e. use tVNS or sham + mindfulness for at least 10 minutes/day at least 4 days/week for 2 weeks)?

Research question 3.2: What are the barriers and facilitators to adherence with the combined intervention?

Hypothesis 3.3: The combined intervention will be well-tolerated and receive positive acceptability ratings.

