After passing the screening, participants will complete an online survey that will include measures of mood, well-being, pain, daytime sleepiness, and sleep quality (see section 6.6 for specific measures).

These measures are self-report and will establish a baseline for each participant. They will be provided with and trained on the following equipment depending on their group assignment:

- **Brightmind Meditation mobile mindfulness app** (Brightmind Meditation, LLC; <https://www.brightmind.com>): Participants in each of the three active treatment groups (tVNS + mindfulness, sham + mindfulness, and mindfulness-only) will be provided with free access to the Brightmind mobile mindfulness app. During the intake session, they will download the app and complete an orientation to learn its features. They will be asked to practice mindfulness meditation through the app for 10 minutes each evening during the 4-week

intervention phase, with compliance defined as using the app 10 minutes/day for at least 4 days/week.

- **Control task:** Participants in the control group will be provided with the link and instructions for a control task (an online number puzzle: <https://play2048.co/>) that has been used in previous studies of mindfulness apps. They will be asked to engage with this control task for 10 minutes each evening during the 4-week intervention phase, with compliance defined as engaging with the task 10 minutes/day for at least 4 days/week. Participants in the control group will receive free access to the Brightmind mindfulness app after study completion.

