- **Soterix Medical RELifit-Tragus Device** (Soterix Medical Inc.; <https://soterixmedical.com/research/tavns>): Participants in the tVNS + mindfulness and sham + mindfulness groups will be provided with the Soterix Medical RELifit-Tragus device, as well as its accompanying equipment (e.g., device charger, gel, cleaning materials). During the intake session, they will be trained on procedures for using the device, including gel application, electrode placement, and device configuration. Once the research assistant confirms that the participant understands how to apply the electrodes and set the stimulator, the research assistant will demonstrate how to take a picture of the electrode application to check the quality of the application. Participants will be instructed to take a picture that hides the identifying features of the face. Participants will be asked to administer tVNS concurrently with mindfulness practice for at least 4 days per week for the first 2 weeks of the intervention phase. They will be asked to send a picture of the application of the electrodes for each stimulation session. If a picture of the application indicates improper placement, a research assistant will contact the participant via phone or email to review proper form.
- **Fitbit Wristband** (Fitbit LLC): All participants will be provided with a Fitbit wristband for overnight sleep and HRV measurement. They will be instructed on the best method for wearing the band during the initial visit. Participants will be asked to wear the wristband overnight each night for the 4-week intervention phase, with compliance defined as wearing the device overnight at least 4 nights/week.
- **Polar H10 Chest Strap** (Polar Electro; [https://www.polar.com/us-en/products/accessories/h10\\_heart\\_rate\\_sensor](https://www.polar.com/us-en/products/accessories/h10_heart_rate_sensor)): All participants will be provided with a Polar H10 chest strap for HRV measurement during mindfulness practice. They will be instructed on the best method for wearing the chest strap during the initial visit. In addition, the research assistant will assist them in downloading a mobile app for data collection/storage and pairing it with the Polar H10 band for HRV recording. They will be asked to wear the chest strap during at least one mindfulness practice session per week during the 4-week intervention period.

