After receiving study equipment and completing training procedures, participants will begin the intervention phase at home. They will be provided with written and/or video instructions as a reminder of procedures for the intervention phase depending on their group (summarized in **Table 1**). Study staff will also be available to answer questions or provide reminders via email and/or phone. During the intervention phase, participants will complete brief weekly online surveys consisting of some of the measures administered at baseline (see section 6.6). The survey will be sent via an electronic link to participants' email address or phone number. At the completion of the 4-week intervention phase, the research assistant will coordinate with the participant to schedule a time to return study equipment and distribute participant payment. Participants will be compensated for their time and effort (see section 10).

Group	Intervention Phase Procedures
-------	-------------------------------

tVNS + mindfulness (n = 20)	
 
- Practice mindfulness meditation through the Brightmind Meditation app for 10 minutes each evening for 4 weeks
 
- Administer tVNS concurrently with mindfulness practice at least 4 days per week during the first 2 weeks of the intervention phase
 
- Wear the Polar H10 chest strap during mindfulness practice at least 1x/week
 
- Wear the Fitbit overnight for 4 weeks
 

Sham + mindfulness (n = 20)	
 
- Practice mindfulness meditation through the Brightmind Meditation app for 10 minutes each evening for 4 weeks
 
- Administer sham stimulation concurrently with mindfulness practice at least 4 days per week during the first 2 weeks of the intervention phase
 
- Wear the Polar H10 chest strap during mindfulness practice at least 1x/week
 
- Wear the Fitbit overnight for 4 weeks
 

Mindfulness only (n = 20)	
 
- Practice mindfulness meditation through the Brightmind Meditation app for 10 minutes each evening for 4 weeks
 
- Wear the Polar H10 chest strap during mindfulness practice at least 1x/week
 
- Wear the Fitbit overnight for 4 weeks
 

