*Positive and Negative Affect Schedule (PANAS):* *Positive emotions* (overall, serenity, joviality, self-assurance) and *negative emotions* (overall, sadness, fear, hostility) will be

measured with 17 adjectives each. This measure will be used to assess changes in self-reported emotions. This measure may be administered at intake, weekly, and at follow-up.

*Multidimensional Assessment of Interoceptive Awareness-2 (MAIA-2).* Interoceptive awareness will be assessed as a potential proximal outcome of mindfulness practice. We will use the body listening (3 items), trusting (3 items), and self-regulation (4 items) subscales (10 items total). These subscales may be administered at intake, weekly, and at follow-up.

*Applied Mindfulness Process Scale (AMPS).* The AMPS scale measures mindful emotion regulation – decentering, positive emotion regulation, and negative emotion regulation. This measure will be used to assess for changes in mindful emotion regulation associated with longitudinal use of the mindfulness app. The 15-item scale may be administered at intake, week 2, week 4, and follow-up.

The Nondual Awareness Dimensional Assessment - State (NADA-S). This 3-item scale measures mindfulness-related processes of self-transcendence. We use it to assess changes in self-transcendence associated with the use of the mindfulness app. The scale is administered at intake, weekly, and at follow-up.

*PERMA Profiler.* This questionnaire measures flourishing across 5 domains: positive emotion, engagement, relationships, meaning, and accomplishment following [name] well-being theory. We will use this 19-item measure to assess for changes in self-reported well-being. This measure may be administered at intake, week 4, and at follow-up.

*Pain Numeric Rating Scale:* Participants will be asked to rate their current pain level on a scale from 0-10 (0 = no pain at all, 10 = highest level of pain imaginable), as tVNS and mindfulness may provide pain relief. This measure may be administered at intake, weekly, and at follow-up.

*System Usability Survey (SUS).* This is a standard version of a usability scale. Participants will be given 10 statements regarding the usability of the equipment they used, and they will report how much they agree with each statement on a 1 – 5 scale. This measure will only be given after the completion of the intervention phase (week 4).

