*Acceptability of Intervention Measure (AIM), Intervention Appropriateness Measure (IAM), and Feasibility of Intervention Measure (FIM).* These brief 4-item scales measures the degree to which participants believe an intervention is acceptable, appropriate, and feasible. These measures will only be given after the completion of the intervention phase (week 4).

**Physiological.** Subjects will be given a Fitbit brand wristband that offers real-time physiological data acquisition to use to monitor their sleep quantity, quality, and overnight heart rate variability (HRV) during the intervention phase. Participants will also be given a Polar H10 chest strap to use during mindfulness sessions, measuring their momentary HRV. Participants may be provided a preassigned account and password for these wearable devices, which may be accessed by the research team to manage raw data.

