#### **Analysis Plan.**

- To analyze feasibility data, we will qualitatively examine rates of recruitment and drop out/attrition and compare them to prior research. Quantitatively, to examine whether dropout is selective, participants who completed the study will be compared to participants who dropped out on group via chi-square independence test. To analyze acceptability data, outcomes regarding tolerance and acceptability will be compared between the groups via

ANOVA. In addition, we will perform thematic analysis of participant responses to open-ended questions about feasibility and acceptability.

- To examine trajectory of sleep and mental health/well-being over time, multilevel modeling (MLM) analyses will be conducted using unrestricted full information maximum likelihood in R via the “lme4” package. Separate models will be conducted using each sleep and mental health/well-being outcome measure as a dependent variable. Linear and quadratic time trends will be estimated, and intervention group will be included as a moderator. To examine adherence, the number of minutes participants spend engaged with the app or tVNS device per week will be averaged. Then, an MLM will be conducted using average weekly engagement as the dependent variable and time (linear and quadratic) and group as predictors. Retention rates between intervention groups will be compared using an independent samples t-test.

**Nerve Stimulation.** The auricular branch of the vagus nerve projects to the brainstem and is accessible via electrical stimulation through surface electrodes. Stimulation produces vagus sensory evoked potentials not induced with off-target stimulation.

**Earpiece Placement:** All subjects will be instructed to place the Soterix device earpiece on their left ear such that the stimulation electrode is positioned over the inner tragus and the return electrode is positioned just anterior to the tragus to minimize off-target stimulation per local pilot protocol (see Figure 2). Subjects will demonstrate their ability to set up the stimulator—including earpiece placement—and text the picture of the electrode placement with their faces occluded, similar to Figure 2. Research assistants will also provide a link with an instructional video that participants can refer to in order to ensure they have properly placed their electrodes. Participants will be asked to send a photo of their electrode placement for each stimulation session via SMS.

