## 7. Possible Discomforts and Risk

**7.1 Transcutaneous Vagal Nerve Stimulator.** Previous studies using some form of stimulation found that some side effects may occur including itching, redness, discomfort, and tingling/mild pain at the stimulation site. These side effects usually end shortly after stopping stimulation. If the electrodes are not well placed then participants might experience mild pain, although the researchers will adjust the electrode placement if this happens. Researchers will also explain how to adjust electrodes for when the subjects are at home. Other less common potential side effects (observed in <1% of study populations) include nausea, headache, heart palpitations, dizziness, vocal hoarseness, and nasopharyngitis. It is important to note that these less common side effects were primarily found in studies of clinical populations with a variety of stimulation methods (e.g., cervical stimulation, bilateral stimulation, longer lengths of stimulation) that are not being used in this study. Thus, while these side effects have been observed in some prior studies, we do not anticipate that are likely to occur in this study of healthy college students.

We will be using a Soterix Medical taVNS device. Their website describes the device safety thusly:

*“taVNS on the other hand, delivers electrical stimulation to the auricular branch of the vagus nerve (ABVN), an easily accessible target that innervates the human ear (Peukar*

*and Filler 2002). Over the last decade, several groups have demonstrated the safety and tolerability of this method, including central and peripheral nervous system effects, and behavioral effects in neuropsychiatric populations (Kreuzer et al 2012, Clancy et al 2014, Rong et al 2016, Bauer et al 2016). taVNS is also being explored in individuals to enhance cognitive and social functioning (Jacobs et al 2015, Jongkees et al 2018, Colzato et al 2018). Furthermore, side-effects of taVNS are minimal, with skin irritation or redness being the most common side-effect. In a review of 51 studies with 1322 human participants receiving tVNS, the most common side effect was local skin irritation (%18). Authors conclude tVNS is well tolerated and safe (Redgrave et al., 2018).”*

- Peuker, E.T., & Filler, T.J. The nerve supply of the human auricle. *Clinical Anatomy*. 15 (1), 35-37 (2002).

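### Hypothesis 3.3 and the planned comparison of tolerance have no direct measure of how participants tolerate home stimulation

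*Combined protocol and SAP*

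**What the plan says.** Section 5, Hypothesis 3.3, makes two separate claims: "The combined intervention will be well-tolerated and receive positive acceptability ratings". The Analysis Plan in section 6.6 carries both forward: "outcomes regarding tolerance and acceptability will be compared between the groups via" ANOVA. Neither place names a tolerance instrument, a time point or a threshold.

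On what is collected and when:

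- **Stimulation period.** Section 6.2 asks for stimulation alongside mindfulness practice "at least 4 days per week for the first 2 weeks of the intervention phase".
- **Weekly surveys.** Section 6.2 says that "participants will complete brief weekly online surveys consisting of some of the measures administered at baseline". The baseline survey, completed before equipment training, holds "measures of mood, well-being, pain, daytime sleepiness, and sleep quality".
- **Pain scale.** Section 6.6 states: "Participants will be asked to rate their current pain level on a scale from 0-10". The reason given is possible pain relief.
- **Usability and acceptability.** Section 6.6 reserves SUS and the AIM, IAM and FIM scales for week 4, at the end of the intervention phase.
- **Calibration.** Section 6.6 has staff ask about sensation and discomfort at each step of the intake ramp. Only afterwards is intensity set to 80% of the discomfort threshold (active) or near 0% (sham).
- **Expected side effects.** Section 7.1 lists local skin symptoms and some rarer systemic ones, and adds: "These side effects usually end shortly after stopping stimulation".

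**The concern.** A hypothesis and a planned test both need a tolerance outcome, and no listed measure supplies one for the two weeks in which participants stimulate at home. Analysts cannot reconstruct symptoms that nobody asked about. Followed as written, the statement that the intervention was well tolerated would rest on acceptability or usability ratings from those still present at week 4, on indirect indicators, or on whatever participants chose to mention.

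The informative contrast is active against near-zero sham, because sham gives the background rate of ear and general symptoms. That contrast needs the same question put to both arms while stimulation is under way. The study is meant to inform later trials of the combined approach, so the side-effect profile is one of the things that a later team would look for here.

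**Working it through.** The plan states no figure for tolerability, so there is none to reproduce. The check has two parts.

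**1. Could any described source serve as the tolerance outcome?**

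| Source (section) | When | Why it does not measure tolerance of home stimulation |
|---|---|---|
| Weekly surveys (6.2) | Weeks 1 to 4 | Described as drawn from baseline measures; no stimulation-symptom item is listed |
| Pain rating (6.6) | Weekly | General pain at the moment of answering, included for relief; silent on itching, redness, dizziness and palpitations |
| PSS, PANAS, GAD-7 (6.6) | Weekly or week 2 | Distress from any cause |
| SUS, AIM, IAM, FIM (6.6) | Week 4 only | Usability, acceptability, appropriateness, feasibility; week 4 minus week 2 = 14 days after planned stimulation ends |
| Calibration questions (6.6) | Intake | Asked before the active and sham settings diverge |
| Dropout and retention by group, minutes of app or device use (Analysis Plan) | Whole study | Give no reason for stopping |
| Open-ended questions (Analysis Plan) | Not stated | Feasibility and acceptability, analysed thematically; no score for an ANOVA |
| Placement photographs (6.2) | Each session | Check electrode position |
| Team meetings (7.6) | Regular | No side-effect question or record described |

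The number of listed instruments that directly measure tolerance of home stimulation is 0.

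**2. What would a direct question yield?**

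Inputs: 20 participants in each stimulation arm (section 6.2, Table 1), and the 18% local skin irritation quoted in section 7.1. The 18% comes from a review of mixed devices, so its use here is an assumption.

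- Expected active participants with irritation: 20 × 0.18 = 3.6.
- Chance of at least one case: 1 − 0.82^20 = 0.981.
- For a symptom at 1%, the upper end of the rarer group in section 7.1: 1 − 0.99^20 = 0.182.
- Upper limit of the exact two-sided 95% interval if 0 of 20 report a symptom: 1 − 0.025^(1/20) = 0.168.
- Power to separate 18% active from an assumed sham rate of 1%, 5% or 10% at 20 per arm (two-sided 0.05, normal approximation, rough at these counts): about 45%, 25% and 11%.

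A checklist would very probably pick up the common local effects. It would usually miss the rare ones and could not support a formal comparison of arms.

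**The case against.** The other side has real substance. The combined intervention includes mindfulness, which the Abstract itself links to early distress and dropout, so the distress scales do bear on tolerance. Dropout, retention and device minutes are numeric indicators of behaviour under treatment. Section 6.6 is also not a closed list: it says which tests may be used, and the Analysis Plan relies on open-ended questions that it never lists.

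A reader might therefore go too far in three ways.

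- **That the trial will hold no information on tolerance at all.** The indirect sources above exist. What is missing is one that identifies stimulation side effects.
- **That home symptoms will go unasked and unrecorded.** The supplied text only fails to specify this. Consent pages and participant instructions were not available, and section 6.2 makes staff reachable by email or phone.
- **That someone who stops stimulating contributes nothing.** A participant who stops but stays can still complete the week 4 scales and shows fewer device minutes; one who leaves enters the dropout comparison.

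It is also fair to say that 20 per arm cannot establish good tolerability firmly. That argues for descriptive reporting; it does not argue against asking. None of these points supplies the score that the planned ANOVA needs.

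**Conclusion.** The point stands as a gap in definition and collection. The protocol promises a tolerance result and specifies acceptability, usability and general well-being measures in its place. The gap is moderate: it affects one of the two claims in Hypothesis 3.3 and one planned comparison, and leaves the sleep and mental health outcomes untouched.

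The conclusion rests on reading the weekly surveys as section 6.2 describes them, and on no side-effect form existing in material that was not supplied. If such a form exists, the remedy reduces to naming it in section 6.6 and in the Analysis Plan. The 3.6 expected cases and the 98% depend on the borrowed 18% rate; the 16.8% limit depends only on 20 participants answering.

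**What to change.** Add to section 6.6:

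> Stimulation side-effect checklist, identical wording in the tVNS and sham arms, in the week 1 and week 2 surveys and whenever a participant stops stimulation or withdraws. Yes/no for redness, itching, tingling or pain at the site, other discomfort, headache, dizziness, nausea, palpitations and hoarseness; worst severity 0 to 10; whether any session was stopped because of symptoms.

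In the Analysis Plan:

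> Tolerance is the proportion of participants with any symptom, and the worst severity, reported descriptively for tVNS and sham, with exact 95% confidence intervals for the proportions. ANOVA is used for the acceptability scores only.

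**Cost.** 40 participants × 2 surveys = 80 short completions inside surveys already planned, plus any at stopping or withdrawal. Prompting will raise symptom reports in both arms, and the sham arm shows by how much. Asking about sensations may lead some participants to guess their arm; identical wording limits this but does not remove it.

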Control (n = 20)	
 
- Engage with the control task for 10 minutes each evening for 4 weeks
 
- Wear the Polar H10 chest strap during the control task at least 1x/week
 
- Wear the Fitbit overnight for 4 weeks
 

**Table 1.** Intervention phase procedures for each experimental group.

**6.3 Subjects.** This study utilizes a between-participant design and will recruit 80 healthy college students aged 18 – 30. Pregnant women may not participate in this study—pregnancy tests provided by the study will be used for women of child-bearing age randomized to a tVNS group prior to starting the study and after the consenting process. Pregnancy tests will only be given in the intake session.

**6.4 Recruitment and Retention.** We will recruit a volunteer sample of undergraduate students from the Gainesville, Florida community who are interested in managing stress. We will post IRB-approved flyers around the community and on the UF campus. The flyers include a survey link where interested students can provide their contact information if they believe they qualify for the study to allow study staff to contact them to schedule an intake appointment. The investigators will be involved in recruitment of participants from multiple sources, including campus tabling events, posting flyers on UF campus and through GatorWell, emails to relevant listservs, making announcements during undergraduate classes, and through word of mouth. The investigators will also post announcements to Facebook and Twitter (see Social Media Strategy). Subjects will be expected to provide their own means of transportation.

**6.5 Inclusion/Exclusion Criteria.** Participants will include adults between the ages of 18-30, consistent with the typical college population. Participants must own a smartphone, be able to read and write English, and not be in ongoing psychotherapy.

Major medical illnesses including diagnosed severe neurological illnesses (e.g., stroke, seizure history), medical conditions associated with neurological effects (e.g. heart, kidney disease), autoimmune disorders, and severe psychiatric diseases (e.g., schizophrenia) will be excluded. Participants with any history of brain surgery, tumor, intracranial metal implantation, pacemakers or other implanted devices will be excluded. These elements will be assessed via self-report.

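### Fitting the multilevel models by full maximum likelihood, with no small-sample method stated, makes standard errors about 1–3% too small: a minor and cheaply corrected optimism

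*Combined protocol and SAP*

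**What the plan says.** Section 6.6, Analysis Plan, names the estimator and the software. Multilevel "analyses will be conducted using unrestricted full information maximum likelihood in R", with `lme4` as the package. The scope is one model per outcome: "Separate models will be conducted using each sleep and mental health/well-being outcome measure as a dependent variable". On the mean structure it says "Linear and quadratic time trends will be estimated, and intervention group will be included as a moderator", which is three coefficients per arm, or 12 in a four-arm model. Adherence is also to be analysed by a multilevel model: "an MLM will be conducted using average weekly engagement as the dependent variable and time (linear and quadratic) and group as predictors". The estimator is not restated there, so it apparently carries over.

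Other analyses use different methods. For acceptability, "outcomes regarding tolerance and acceptability will be compared between the groups via" ANOVA. For selective dropout, "participants who completed the study will be compared to participants who dropped out on group via chi-square independence test". Retention is compared by a t-test.

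Section 6.3 says the study "will recruit 80 healthy college students", and Table 1 gives 20 in each of four groups.

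The plan does not state a significance level, the random-effects structure, a degrees-of-freedom method, or how p-values and intervals will be obtained from the multilevel models.

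**The concern.** ML divides sums of squares by the full number of independent units. It ignores the degrees of freedom spent on estimating arm-specific means and trends. REML makes that correction. If ML standard errors are then referred to a normal or chi-square distribution, the uncertainty in the variance estimates is ignored as well. Both effects act in the same direction: intervals too narrow and tests too liberal.

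Aims 2 and 4 exist to produce effect-size data for later trials, so the stated uncertainty is part of the product. The bias would run the same way in every multilevel model. It also grows as participants drop out, and the protocol's own background treats dropout as a known problem for mindfulness interventions.

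**Working it through.** **The plan's own figure.** 4 × 20 = 80, which agrees with section 6.3. The plan gives no power, standard error or error rate to reproduce.

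**Inputs from the documents.** N = 80 participants and G = 4 arms. Section 6.6 gives T = 4 occasions (for example PSQI, PHQ-8 and GAD-7), T = 6 (for example PSS and PANAS) or T = 3 (PERMA).

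**Assumptions not in the documents.** Two-sided 5% tests, a normal (Wald z) reference of 1.96, balanced data, and 20% dropout where stated, which leaves 64 participants.

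**Case A: random slopes, contrast in individual slopes.** ML divides the between-participant variance by N instead of N − G.

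- Standard error ratio, ML to correct: √((N − G)/N) = √(76/80) = 0.975, so 2.5% too small.
- True error: 2·P(t₇₆ > 1.96 × 0.975) = 2·P(t₇₆ > 1.910) = 6.0%. A nominal 95% interval therefore covers 94.0%.
- Interval width, correct to ML: the t critical value on 76 df is 1.992, and 1.992/1.910 = 1.043, so about 4% wider.
- With 64 participants: √(60/64) = 0.968, so 3.2% too small. The error is 2·P(t₆₀ > 1.898) = 6.2%. The width ratio is 2.000/1.898 = 1.054, so about 5% wider.

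**How much is due to the estimator and how much to the reference distribution (80 participants).** ML with a t reference gives 5.6%. REML with z gives 5.4%. Both together give the 6.0% above. The ML choice alone, which is the part the plan states, therefore leaves an error of about 5.6%.

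**Case B: random intercepts only, complete data.** The relevant variance is now within participants, with N(T − 1) − 2G degrees of freedom.

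| T | N(T − 1) | df | SE ratio | True error |
|---|---|---|---|---|
| 3 | 160 | 152 | 0.975 | 5.8% |
| 4 | 240 | 232 | 0.983 | 5.5% |
| 6 | 400 | 392 | 0.990 | 5.3% |

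So with complete data the range over the two random-effects structures is 5.3–6.0%, and the standard errors are 1.0–2.5% too small.

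**Check by simulation.** Null data were simulated for four arms of 20 or 16, at 4 or 6 occasions, with random intercept and slope and a quadratic mean. The assumed variances were intercept 1, slope 0.3 and residual 0.5, with 2,000 runs per scenario and a Monte Carlo error of about 0.5 points.

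- For the intake-to-week-4 change contrast, the ML/REML standard error ratio was 0.978–0.985.
- ML with z rejected in 4.9–5.2% of runs, against 4.1–4.5% for REML with t on the same data. The gap is informative. The level is less so, because the properly calibrated comparator itself fell below 5% in these runs.
- The 6-df ML likelihood-ratio test of group by time rejected in 5.5–6.4%.
- A larger simulation of 20,000 runs per scenario, for the linear-trend contrast with 80 participants, gave 6.0–6.2% for ML with z. This agrees with Case A.

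**The case against.** The strongest reply is that the effect is too small to matter for a preliminary study. Take a simple comparison of 20 with 20. The standard error of a standardised difference is about √(2/20) = 0.32, and the 95% half-width is about 0.62 SD. Widening by 4.3% gives 0.62 × 1.043 = 0.647, which is less than 0.03 SD more. No later trial would be planned differently for that. With balanced complete data, ML and REML also give the same fixed-effect estimates, so the effect sizes themselves do not move. ML is the proper choice when nested fixed-effect structures are compared by likelihood ratio. All of this stands and fixes the severity at minor. It does not make the stated error bars right, and the correction costs almost nothing.

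Four stronger readings are tempting, and the documents do not support them:

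- A reader might infer that every outcome is affected. Acceptability, selective dropout and retention use other methods, and the open-ended responses are analysed thematically.
- A reader might infer that the plan has chosen normal-reference tests. It is silent. `lme4` prints no p-values by default, so what is missing is a statement of how tests and intervals will be obtained.
- A reader might take 20 per arm as the effective sample size. In a four-arm model the variance components are pooled over all 80.
- A reader might quote 6.4% (40 participants) or 6.7% (32 participants). Those figures need models restricted to two arms. The hypotheses in section 5 are pairwise, but the Analysis Plan separates models by outcome, with group as a moderator, and describes no two-arm model.

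**Conclusion.** The point holds, at minor severity. Full ML is a written choice, and it biases the standard errors in the multilevel models downward by about 1–3% at this sample size. No small-sample method is stated that would limit the effect on tests and intervals.

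The error rates of 5.3–6.0% (complete data) and about 6.2% (20% dropout, random slopes) depend on a two-sided 5% level, a normal reference and balanced data, none of which the plan specifies. The upper end requires random slopes, and the plan does not state its random effects. The direction is the same in every affected model, but the size would not by itself overturn a conclusion.

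**What to change.** Add to the Analysis Plan that estimates, confidence intervals and tests from the multilevel models will be reported from REML fits with Kenward-Roger or Satterthwaite degrees of freedom, and that maximum likelihood will be used only for likelihood-ratio comparison of fixed-effect structures. State in the same place the significance level, the random effects, and whether the adherence model follows the same rule.

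The cost is one or two sentences and a standard R add-on package. No new data are needed, and incomplete outcomes are still handled under the missing-at-random assumption that the likelihood approach implies. The only downside is slightly wider intervals, by up to about 4–5% in the cases above.
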